# 9. GENERAL ISSUES FOR STATISTICAL ANALYSIS

# 9.1 Definitions, Derived Variables and Datasets

Definitions of indicators and methods to derive variables are described in the relevant sections of this document. Datasets will be derived from the database used to record the information gathered through the e-CRF.

## 9.1.1 Baseline Values

The values assessed at Visit 1, before the first product administration, will be considered as baseline values.

## 9.1.2 Duration of Exposure

Total duration of subject participation was of about 12 months. Total duration of the study was expected to be about 15 months.

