7.1 Allowed Medications and Treatments

All topical drugs (any topical midriatic treatment and any traditional topical therapy for uveitis) will be admitted for the treatment of the signs and symptoms associated with HLA-B27-associated chronic relapsing uveitis.

In the case of relapse with LFM values are > 100 ph/ms despite treatment with topical therapy, or in any case the LFM values result to be > 100 ph/ms, then a systemic therapy is recommended and the subject has to be dropped-out from the study and treated according to the best medical judgement.

7.2 **Prohibited Medications and Treatments**

The following medications are prohibited during the study and the administration will be considered a protocol violation: supplements and nutraceuticals, systemic therapies for uveitis (anti-inflammatory, immunosuppressive, biologicals), hormonal contraceptives, long-term treatment with systemic anti-inflammatory, immunosuppressive or biological drugs for other diseases different from uveitis. Systemic therapies with anti-inflammatory, immunosuppressive drugs are allowed for reasons different from uveitis and in any case for periods not exceeding 15-30 days.

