10.4 Additional Unscheduled Visits in Case of Relapse

Should a relapse occur, an unscheduled visit will be performed including a complete ophthalmic evaluation. The number of cells in the AC will be determined by slit lamp, too.

Topical or systemic treatment will be prescribed to the subject according to the severity of the relapse and according to the best medical judgement.

Two following visits will be scheduled 2 and 6 weeks thereafter. During these visits a complete ophthalmic evaluation will be done.

If the subject is prescribed a systemic treatment for the relapse, he/she will be withdrawn from the study, and treated according to the best medical judgement.

If only topical treatments are prescribed, the subject will be allowed to continue the study. Depending on the onset time of the relapse it could be necessary to delay Visit 2 or Visit 3 around 2 months after the topical treatment conclusion.

Should Visit 2 be delayed, the delay will be recovered by keeping the date of Visit 3 at 12 months.

Should Visit 3 be delayed, the delay will not be recovered.

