## 12.1 Extent of Exposure

The extent of exposure will be estimated on the treatment duration.

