### **12.2** Adverse Events

Adverse event will be coded using the last updated version of the Medical Dictionary for Regulatory Activities (MedDRA) dictionary to give a preferred term (PT) and a system/organ class term (SOC) for each. Adverse events will be tabulated by treatment group. Tables will be included the number of patients who experienced at least one AE, of study product-related AEs (defined as definitely, probably, possibly, or unrelated), of serious AEs, and the number of patients withdrawn due to AE, summarized by treatment arm. Comparisons between treatment arms will be performed using chi-square test.

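### Patient-level exposure is not derived and adverse events are compared as crude proportions, although follow-up can fall short of or exceed 12 months

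*SAP*

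**What the plan says.** SAP 9.1 promises that variable derivations appear in the relevant sections. SAP 9.1.2 then offers nominal lengths only: "Total duration of subject participation was of about 12 months", and about 15 months for the whole study. SAP 12.1 adds one sentence, "The extent of exposure will be estimated on the treatment duration", without a derivation. The output list in SAP 14 has no exposure table.

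For AEs, SAP 12.2 (like protocol 14.5) tabulates "the number of patients who experienced at least one AE", with product-related and serious AEs alongside, and states "Comparisons between treatment arms will be performed using chi-square test". No person-time, rate or time-to-event summary is planned.

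Other sections make follow-up uneven:
- Protocol 7.1: when flare exceeds 100 ph/ms, "the subject has to be dropped-out from the study".
- Protocol 10.4: "If the subject is prescribed a systemic treatment for the relapse, he/she will be withdrawn from the study".
- Protocol 10.4 also allows a relapse to postpone Visit 3 until around two months after topical treatment ends, and adds "Should Visit 3 be delayed, the delay will not be recovered".
- Protocol 14.7 and SAP 7 expect 20% dropout over 12 months.
- Protocol 11.2 replaces patients who leave for systemic therapy. SAP 8.3 keeps every eligible randomised patient with at least one dose in the safety set, so both the leaver and the replacement count.

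**The concern.** A crude proportion is easy to read as a 12-month risk only if nearly everyone is observed for about 12 months. Here a relapse can end participation early or prolong it, and relapse is the outcome the product is meant to change. Observation time may therefore depend on treatment, and a chi-square test on counts can neither show nor correct that. Without a derived exposure variable, the reader of the safety tables cannot tell whether the arms had similar time in which to report an AE.

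**Working it through.** **Plan's own figures.** The documents give no AE rate and no exposure total to reproduce. The nearby sample size does reproduce: a t-test for a difference of 0.6 with SD 0.7, 80% power and two-sided 5% (sidedness assumed) needs 22.4, so 23 per arm, or 46. Then 46 / 0.80 = 57.5, or 58, against 60 recruited. These figures are not in dispute. Only the 20% dropout and the 30 per arm are carried forward.

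**Assumptions.** True 12-month AE risk R of 10%, 20%, 40% or 60%, equal in both arms. Constant hazard h = -ln(1 - R). Dropouts (share d) leave evenly over the year and are not observed afterwards. A share e has follow-up extended by x years. None of these except the overall 20% dropout is in the documents.

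**Formula.** A dropout reports an AE with probability 1 - R/h, and an extended patient with probability 1 - (1 - R)^(1+x). So

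crude = d(1 - R/h) + e[1 - (1 - R)^(1+x)] + (1 - d - e)R.

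Example with R = 0.20, d = 0.20, e = 0: h = 0.2231, 1 - 0.20/0.2231 = 0.1037, crude = 0.20 × 0.1037 + 0.80 × 0.20 = 0.1807. Mean follow-up is 0.80 × 1 + 0.20 × 0.5 = 0.90 years.

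**Crude proportion (%) and its departure from R (points)**

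| Scenario | R = 10% | 20% | 40% | 60% |
|---|---|---|---|---|
| 20% dropout | 9.0 (-1.0) | 18.1 (-1.9) | 36.3 (-3.7) | 54.9 (-5.1) |
| No dropout, 20% of patients extended 4 months | 10.6 (+0.6) | 21.2 (+1.2) | 41.9 (+1.9) | 62.1 (+2.1) |

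The loss of 0.10 years from 20% dropout is offset in mean follow-up if 0.10 / (4/12) = 30% of patients are extended by 4 months, or 0.10 / (2/12) = 60% by 2 months.

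**Spurious difference, active minus placebo (points), with no true difference**

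| Scenario | R = 10% | 20% | 40% | 60% |
|---|---|---|---|---|
| 20% dropout in both arms | 0 | 0 | 0 | 0 |
| Dropout 10% active, 30% placebo (0.95 and 0.85 years) | +1.0 | +1.9 | +3.7 | +5.1 |
| Dropout 10% in both; 4-month extension in 10% active, 40% placebo (0.98 and 1.08 years) | -0.9 | -1.7 | -2.8 | -3.2 |

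**Sampling error.** The standard error of the difference is sqrt(2R(1 - R)/30): 10.3 points at R = 20% and 12.6 at 40% and 60%. At R = 10% it is sqrt(0.18/30) = 7.7 points. The largest spurious difference above is 5.1 / 12.6 = 0.4 of a standard error.

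**The case against.** A reader might infer that the SAP assigns 12 months of exposure to every patient. It does not. SAP 9.1.2 says about 12 months and describes participation, while SAP 12.1 points to treatment duration. What is missing is the derivation.

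A reader might also infer that 12-month risk must be understated. Early exit does lower the crude proportion, but the Visit 3 delays raise it. Protocol 11.1 and SAP 9.1.4 encourage patients who stop treatment to complete the remaining visits, and protocol 13.1 records AEs off product, so stopping treatment need not end AE observation.

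A third inference is that the arms will be compared over unequal time, to the product's disadvantage. No withdrawal figures by arm exist, and equal withdrawal produces no difference. If placebo patients relapse more often, withdrawal shortens their time and Visit 3 delay lengthens it, so even the sign is open. Nor do the documents show that most early exits come from relapse: eight reasons for discontinuation are listed without frequencies.

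Larger effects follow if a big share of relapses ends participation. At the sizing rates of 2.0 and 2.6 relapses per year, a 25% share would mean exits of 1 - exp(-0.5) = 39% and 1 - exp(-0.65) = 48%, well above the 20% allowance. The documents do not say whether that allowance includes the systemic-therapy exits, which are replaced.

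Finally, crude AE proportions are a common display, and this is a 60-patient trial with an exploratory aim and safety as a secondary objective. That limits the weight of the point but does not answer it. SAP 5.3 names AE incidence as an endpoint, and nothing planned shows the time over which it accrues.

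**Conclusion.** The point holds in limited form. Exposure is not operationally defined, it is not linked to the AE tables, and no time-adjusted AE summary is planned although follow-up can vary in both directions. The likely distortion is about 1 to 5 percentage points, either in the proportion within an arm (20% dropout) or in the comparison (a 10% versus 30% split). These sizes rest on assumed risks, exit timing and splits by arm, and on no observation after dropout. At 30 per arm they would seldom change a conclusion. The change is still worth making, because it is cheap and because an uncertain direction can be settled only by measuring the time.

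**What to change.** In SAP 9.1.2 and 12.1, derive for each patient:
- exposure = last dose date minus first dose date plus 1;
- AE observation time = first dose to last AE contact.

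Summarise both by arm. The second variable is needed because protocol 13.1 records AEs off product and protocol 13.4.2 collects serious AEs for two weeks after the last visit. Time on product would be the wrong denominator for those events.

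In SAP 12.2, keep the crude proportions. Beside them, for any AE, related AEs and serious AEs, report the rate per patient-year of AE observation time by arm, with the difference and 95% CI, and the 12-month cumulative incidence censored at the end of AE follow-up.

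Protocol 10.4 (withdrawn from the study) must be reconciled with protocol 11.1 and SAP 9.1.4 (remaining visits encouraged after treatment stops), since together they determine when AE observation ends.

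Cost: SAP wording, two derived variables, an exposure table and extra columns in Table 14.3.1, settled before database lock and unblinding. Dose dates are already in the patient diary. The downside is a little more programming and wide intervals for rare events.

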## 9.1.3 Treatment Compliance

Subjects were asked to keep a patient diary noting the day and date when they take the study product and any adverse event they experience. Subjects were asked to bring their patient diary to each study visit along with all used and unused study product containers.

# 9.1.4 Methods for Withdrawals and Missing Data

A subject could be discontinued from the study treatment at any time if either the subject, and/or the investigator, and/or Eye Pharma feel that it is not in the subject's best interest to continue the study treatment. The following is a list of possible reasons for study treatment discontinuation:

- Subject withdrawal of consent
- Subject is not compliant with study procedures

Statistical Analysis Plan Version no. 1.0 - 20/07/2020

Protocol Code NORFLO-ORO-16 EudraCT number NA

- Need for the subject to start a systemic anti-inflammatory, immunosuppressive, biologicals therapy for uveitis or for other pathologies
- Adverse event that indicated in the opinion of the investigator that it would be in the best interest of the subject to discontinue study treatment
- Pregnancy
- Protocol violation requiring discontinuation of study treatment
- Missed follow-up
- Eye Pharma requests early study termination.

All subjects who discontinued the study treatment should come back for an early discontinuation visit as soon as possible and then they should be encouraged to complete all remaining scheduled visits and procedures.

All subjects were free to withdraw from participation at any time, for any reason, specified or unspecified, and

Reasonable attempts were made by the investigator to obtain a reason for subject's withdrawals. The reason for the subject's withdrawal from the study was specified in the subject's source documents.

No missing data will be replaced.

#### Multicenter Studies Considerations 9.2

Analysis will be adjusted for the clinical site. Analyses specific for each clinical site will be considered, based on the number of subjects enrolled in each clinical site.

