8 ENROLLMENT, TREATMENT ASSIGNMENT AND BLINDING

8.1 Method of Assigning Subjects to Treatment Groups

Up to 60 eligible patients will be randomly assigned to NORFLO[®] ORO or placebo treatment groups in a 1:1 ratio using a stratified randomization blocks scheme. The patient randomization list will be generated by Latis S.r.l., using the procedure PROC PLAN of SAS 9.4 for Windows (SAS Institute Inc., Cary, NC, USA).

8.2 **Blinding**

Due to the objectives of the study, the investigators, research staff, or patients will not know the treatment identity (test or control). The following study procedures will be in place to ensure double-blind administration of study treatments:

• Access to the randomization code will be strictly controlled.

Packaging and labeling of test and control treatments will be identical to maintain the blind.

The study blind will be broken on completion of the clinical study and after the study database has been locked.

During the study, the blind may be broken **only** in emergencies when knowledge of the patient's treatment group is necessary for further patient management.

The Principal investigator will receive a study treatment identification key in the form of sealed envelopes containing the kit number and the corresponding treatment.

The envelope can be opened only in case of an emergency presenting the need to disclose the identification of the study treatment assigned to the patient, for the purpose of establishing the appropriate therapy. Once the code is broken for a patient, this patient shall be withdrawn from the study, with the completion of the final study evaluation, indicating the specific reason of the patient withdrawal.

The Study Monitor must be notified immediately by the investigator of any emergency unblinding; the date and time, along with the reason for the unblinding, will be noted. Treatment codes will not be freely available to the investigator or personnel monitoring the study until after the study completion and database lock.

8.3 **Formulation of Test and Control Products**

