10 EVALUATIONS BY VISIT

10.1 Visit 1 (t₀)

- 1. Review the study with the subject (subject's legal representative) and obtain written informed consent
- 2. Assign a unique screening number to the subject
- 3. Record subject's demographics data
- 4. Record subject's medical history, including a history of uveitis, diagnosis date and prior uveitis treatments and the number of relapses during the previous year
- 5. Record subject's concomitant medications
- 6. Perform a physical examination of the subject
- 7. Vital signs collection
- 8. Urine dipstick specific pregnancy test
- 9. Perform a rheumatologic evaluation of the subject
- 10. Perform subject's ophthalmic evaluation (BCVA, Slip lamp, OCT Spectralis[®], LFM, Goldman tonometry).
- 11. Evaluation of uveitis symptoms by VAS (ocular pain, blurry vision, floaters, photophobia)
- 12. Evaluation of the patient's attitude towards the study treatment, through the Quick Questionnaire
- 13. Evaluate inclusion/exclusion criteria adherence
- 14. Randomize subject and dispense study product
- 15. Initiate subject diary.

After about 3 months of treatment the study staff will contact the patient by phone to verify that the study product is correctly taken.

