14.7 Sample Size

In a previous study²⁵, 275 relapses on 106 patients were observed, corresponding to a mean number of relapses per patient of 2.6 (Standard deviation, SD: 0.7) while in the post-treatment group 36 relapses were registered corresponding to a mean number of relapses per patient of 0.34 relapses/patient. With a statistical power of 80% and a significance level (alpha) of 5% and a common SD of 0.7, 46 patients are needed to observe a difference of 0.6 relapses/patients between the two treatment groups (i.e., 2 relapses/patient in the NORFLO[®] ORO treatment group vs. 2.6 in the placebo treatment group). To take into account a potential dropout rate of 20% over 12 months, 60 patients will be recruited. Subjects dropping out the study because they are beginning systemic therapy with anti-inflammatory, immunosuppressive, biologic drugs will be replaced.

A second primary endpoint, i.e. the reduction of mean number of relapses between the year before treatment and the study period, will be examined. No formal sample size estimate is feasible on this endpoint, as it was not tested previously and no reasonable scenario can be drawn.

As the two endpoints will be assessed in a hierarchical order (first, "the mean number and intensity of relapses during the study between treatment groups" and then "the reduction of mean number of relapses between the year before treatment and the study period"), according to the "Points to consider on multiplicity issues in clinical trials", issued by the Committee for Proprietary Medicinal Products (CPMP - 2002), no sample size adjustment for multiplicity is needed.

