# 7. SAMPLE SIZE AND STATISTICAL POWER CONSIDERATION

With a statistical power of 80% and a significance level (alpha) of 5% and a common SD of 0.7, 46 patients are needed to observe a difference of 0.6 relapses/patients between the two treatment groups (i.e., 2 relapses/patient in the NORFLO® ORO treatment group vs. 2.6 in the placebo treatment group). To take into account a potential dropout rate of 20% over 12 months, 60 patients were recruited.

A second primary endpoint, i.e. the reduction of mean number of relapses between the year before treatment and the study period, will be examined. No formal sample size estimate was feasible on this endpoint, as it was not tested previously and no reasonable scenario can be drawn.

As the two endpoints will be assessed in a hierarchical order (first, "the mean number and intensity of relapses during the study between treatment groups" and then "the reduction of mean number of relapses between the year before treatment and the study period"), according to the "Points to consider on multiplicity issues in clinical trials", issued

Statistical Analysis Plan Version no. 1.0 – 20/07/2020 Protocol Code NORFLO-ORO-16 EudraCT number NA

by the Committee for Proprietary Medicinal Products (CPMP - 2002), no sample size adjustment for multiplicity was needed.

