## 11.4 Efficacy Analysis

## 11.4.1 Primary Efficacy Endpoints

The number and intensity of relapses were assessed through instrumental analysis and physical examination. These endpoints will be assessed from baseline to end of treatment.

When a relapse occurs, the data reported in the first unscheduled visit concerning the intensity of the relapse and data from LFM will be used as they are taken before the administration of both systemic and topical cortisone.

Mean and standard deviation will be used to describe the number of relapses per patient. The mean number of relapses per patient will be compared between the treatment groups using Student's t-test. ANOVA will be used to include predictive/confounding variables in the model.

In addition, a generalized linear mixed model (GLMM) with Poisson statistical distribution and with the number of relapses as dependent variable will be used to assess the effects of the treatment on reducing the number of relapses, also including in the model other potentially predicting/confounding variables.

The intensity of each relapse will be scored as mild (either trace to 1+ cell OR flare  $\leq 20$ ), moderate (2+ to 3+ cell OR Flare  $\geq 20$  and  $\leq 100$ ) and severe (4+ cell OR Hypopyon OR flare  $\geq 100$ ). For each patient, the average intensity will be estimated as the mean of the intensity of relapses observed during the study. The average and the maximum intensity will be compared between treatment groups using Student's t-test. ANOVA will be used to include predictive/confounding variables in the model. As this variable could likely be not normally distributed, Wilcoxon Mann-Whitney will be also used.

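### No deciding model or covariate set is named for the between-arm relapse count, and the t-test that sized the trial cannot carry the site adjustment stated in SAP 9.2

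*SAP*

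**What the plan says.** - **Site.** SAP 9.2 gives a general rule, tied to no endpoint or model: "Analysis will be adjusted for the clinical site".
- **Relapse count.** SAP 11.4.1: "The mean number of relapses per patient will be compared between the treatment groups using" Student's t-test. An ANOVA follows, to bring in predictors or confounders, and then a Poisson mixed model with further such variables. None of these variables is named. The table in SAP 11.5 lists the three methods together and ranks none. Protocol 14.3 has the same structure.
- **Randomisation.** Protocol 8.1 allocates patients "in a 1:1 ratio using a stratified randomization blocks scheme". SAP 4.3 repeats this. Neither names a stratification factor.
- **Baseline count.** Protocol 10.1 records "the number of relapses during the previous year" at Visit 1. SAP 11.4.1 uses it in the within-group paired t-test and in the median-split responder classification. No between-arm model of relapse count names it.
- **Contrast.** SAP 11.4.1 and 11.4.2 do name the baseline value as covariate in the ANCOVAs for laser flare, IOP, OCT, BCVA and VAS symptoms.
- **Sample size.** SAP 7: "With a statistical power of 80% and a significance level (alpha) of 5% and a common SD of 0.7, 46 patients are needed", for "2 relapses/patient in the NORFLO® ORO treatment group vs. 2.6 in the placebo treatment group".

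**The concern.** The lead primary endpoint is specified less fully than the secondary ones. Three things follow.

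1. **Choice among results.** SAP 9.3 makes no multiplicity adjustment because the primary endpoints are tested in order. An ordered procedure needs one pass-or-fail result at its first step. With three methods and open covariate lists, that result is undefined for the relapse count, and a favourable one could be chosen once the data are seen.
2. **Site and strata.** A two-sample t-test has no place for site or for stratification factors. If those factors predict relapses, the t-test uses a standard error that is too wide for the design.
3. **Baseline count.** A predictor already collected in a 60-patient trial is not secured for the main comparison.

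**Working it through.** **Inputs from the documents.** Alpha 5%, power 80%, SD 0.7, difference 2.6 − 2.0 = 0.6, 46 evaluable, 20% dropout, 60 recruited (Protocol 14.7, SAP 7); four sites (Protocol Synopsis). Sidedness is not stated and two-sided is assumed. A one-sided test would need only 17 per arm by the normal approximation.

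**Step 1. Reproduce the plan's figure.** Unadjusted two-sample t-test with n per arm: noncentrality = 0.6 / (0.7 × √(2/n)), df = 2n − 2.
- n = 22: 0.6 / (0.7 × 0.3015) = 2.84, power 79.3%.
- n = 23: 0.6 / (0.7 × 0.2949) = 2.91, power 81.1%.

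So 23 per arm, 46 in total, is the smallest size that reaches 80%, exactly as stated. For dropout, 46 / (1 − 0.20) = 57.5, rounded up to 58. The stated 60 leaves 60 × 0.80 = 48 evaluable. The trial was sized on the unadjusted comparison, and the figure is sound on its own inputs.

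**Step 2. Fit site and prior-year count.** The documents give no correlation ρ between the prior-year and on-study counts, so ρ is an assumed range that includes zero. Residual SD = 0.7 × √(1 − ρ²). Three site terms and one baseline term cost 4 df, so df = 44 − 4 = 40. Here site is taken to explain no variance.

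| Assumed ρ | Residual SD | Power, 46 evaluable | Total N for 80% |
|---|---|---|---|
| unadjusted | 0.700 | 81.1% | 46 |
| 0 | 0.700 | 81.0% | 46 |
| 0.2 | 0.686 | 82.5% | 44 |
| 0.3 | 0.668 | 84.5% | 42 |
| 0.4 | 0.642 | 87.2% | 40 |
| 0.5 | 0.606 | 90.6% | 36 |

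**Step 3. Ignore a prognostic stratum.** Simulation with 20,000 runs and normal outcomes: 48 patients, four equal sites, 1:1 within site, total SD 0.7. It assumes that site is a stratum, which the documents do not say, and it assumes the share of variance that site explains.

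| Variance explained by site | True alpha, t-test | True alpha, adjusted | Power, t-test | Power, adjusted |
|---|---|---|---|---|
| 0% | 0.051 | 0.050 | 82.5% | 82.4% |
| 10% | 0.039 | 0.049 | 83.5% | 86.1% |
| 20% | 0.027 | 0.047 | 85.2% | 90.2% |
| 30% | 0.019 | 0.050 | 86.5% | 93.5% |

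Ignoring the stratum moves the t-test's error rate down, not up, and only if the stratum is prognostic.

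**Step 4. Choice among results.** This cannot be sized from the documents, because the candidate covariates are not named.

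**The case against.** The strongest defence is that the plan already contains adjusted analyses. SAP 9.2 is a general rule, and the ANOVA or the Poisson model can satisfy it by including site. The open wording would also admit the prior-year count. The gain from that count may be small: entry requires at least one relapse in the last year (Protocol 6.2), which narrows its range, and it is taken from history. At ρ = 0.2 the gain is 82.5 − 81.1 = 1.4 points.

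Much of this stands, and it rules out several stronger readings that a reader might infer:

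- *The t-test is the primary analysis.* It is listed first and matches the sample size, but no section says that it decides the endpoint.
- *SAP 11.4.1 flatly contradicts 9.2.* The two conflict only if the t-test decides. What the text shows is that 9.2 has not been carried through to the relapse analysis.
- *Site is a stratification factor.* No factor is named, so this cannot be assumed.
- *The prior-year count goes unused.* It feeds the paired test and the responder classification.

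The defence does not close the gap. A model that may include site or baseline count is not one that must, and nothing says whether it outranks the t-test.

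**Conclusion.** The point holds as a failure to pre-specify: one endpoint, three listed methods, no deciding one and no named covariate. A reader might go further and infer an inflated t-test error rate or a wrong sample size. The documents support neither: the 46 is reproduced exactly, and leaving out strata can only make the t-test conservative.

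The precision at stake runs from nothing (81.1% unadjusted, 81.0% adjusted at ρ = 0) to about 9 or 10 points (90.6% at ρ = 0.5). Site would add to this only if it is prognostic. The exposure to choice among results is real but cannot be quantified.

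The figures rest on the plan's SD of 0.7, a linear model, two-sided alpha, assumed correlations, and all 46 patients entering the analysis. SAP 5.1 confines the primary analysis to patients with relapses. That is a separate issue and would lower the analysed number.

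**What to change.** SAP 4.3 places unblinding after database lock, so the following can be settled in an SAP amendment before the blind is broken.

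1. Designate one primary model for the between-arm relapse count, for example the Poisson model already planned. Fixed covariates: treatment, site (as 9.2 requires), the actual stratification factors, and prior-year relapse count.
2. State the stratification factors used to build the randomisation list.
3. Close the covariate list. Label the unadjusted t-test and the remaining model supportive.
4. If the Poisson model is chosen, state its random effect and how dispersion is handled. The planned SD implies a variance of 0.7² = 0.49 at a mean of 2.0 to 2.6, well below the Poisson variance, and the power figures above are for a linear model.
5. Align SAP 9.2, 11.4.1 and 11.5 so that each names the same deciding analysis.

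The cost is SAP wording and a few degrees of freedom: four for site and prior count, which is 0.1 point of power if they carry no information, plus any for strata other than site. No new data are needed.
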